Bone marrow aspirates will be collected as clinically indicated to confirm a response of complete response (CR) or stringent complete response (sCR). Subjects with a suspected CR or better will have a bone marrow for MRD assessment at 12 months \pm 4 weeks unless a minimal residual disease (MRD) assessment was performed within 4 months prior to the scheduled assessment (eg, coordinated with a bone marrow procedure to confirm CR). Subjects with a MRD[-]CR at the first time point (8 to 12 months from initiation of treatment) should have the subsequent MRD assessment 12 months \pm 4 weeks after the earlier assessment (20-24 months after the start of treatment), if subjects have not relapsed nor started new antimyeloma therapy prior to this subsequent MRD assessment.

Subjects who discontinue either carfilzomib or pomalidomide, but not both drugs, will be considered to remain on study treatment.

Safety laboratory studies (complete blood counts and differential, complete metabolic panel) will be collected on day 1 of each cycle, prior to dosing. A Data Review Team (DRT) will convene regularly to independently evaluate safety. Timing and frequency of the DRT meetings will be detailed in the DRT charter. After discontinuation of study treatment, a safety follow-up visit will be scheduled 30 (+3) days after the last dose of study treatment. Subjects who discontinue treatment and either start new antimyeloma treatment or have PD, will enter long-term follow-up every 12 weeks until death or end of study.

The overall study design is described by a study schema in Section 2.1. The endpoints are defined in Section 4.1.

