6.4 Screen Failures

Screen failures are defined as subjects who consent to participate in the clinical study but are not subsequently enrolled in the study. A minimal set of screen failure information will be collected that includes demography, screen failure details (reasons for screen failure up to 3), eligibility criteria, and any serious adverse events.

Individuals who do not meet the criteria for participation in this study (screen failure) may be rescreened once. Refer to Section 9.1.1.

Subjects who experience a technical failure of local laboratory samples at screening (for example sample is lost or damaged in transit, or otherwise cannot be analyzed) will not be considered a screen failure. Lab samples may be retested during screening in such cases, subject to the screening window not being exceeded.

7. Treatments

Study treatment is defined as any investigational product(s) or non-investigational product(s) intended to be administered to a study subject according to the study protocol.

Note that in several countries, investigational product and non-investigational product are referred to as investigational medicinal product and non-investigational medicinal product, respectively.

The Investigational Product Instruction Manual (IPIM), a document external to this protocol, contains detailed information regarding the storage, preparation, destruction, and administration of each treatment.

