7.4 Dose Modification

7.4.1 Dosage Adjustments, Delays, Rules for Withholding or Restarting, Permanent Discontinuation

7.4.1.1 Amgen Investigational Product: Carfilzomib

Carfilzomib will be discontinued, temporarily delayed, or dosage temporarily reduced, in the event of a treatment-related toxicity that, in the opinion of the investigator, warrants the discontinuation, temporary delay or dose reduction as indicated in [Table 7-2](#) and [Table 7-3](#) (refer to [Table 7-5](#) and [Table 7-6](#) for KPd pomalidomide dosage adjustments).

Dose reduction levels of carfilzomib for toxicity management of individual subjects are provided in [Table 7-1](#). Subjects who require a dose level reduction and tolerate the reduced dose for 1 full cycle may at the discretion of the treating physician increase the dose to a prior dose starting with the next cycle except when the dose reduction is due to: pulmonary hypertension, pulmonary toxicity, grade 3 or worse cardiac failure, or drug-induced hepatotoxicity.

Table 7-1. Dose Decrements for Carfilzomib

Nominal Dose (mg/m ²)	Reduced Carfilzomib Doses (mg/m ²)			
	Dose -1	Dose -2	Dose -3	Dose -4
20 ^{a, b}	15	11	Discontinue	-
56	45	36	27	20

^a If dose reduction of carfilzomib is required on cycle 1 day 1, the investigator should contact the medical monitor to discuss the situation before any additional doses of carfilzomib are administered.

^b For subjects with baseline chronic hepatic impairment (mild, moderate), reduce the starting and subsequent doses of carfilzomib by 25% (ie, 15 mg/m² day 1 of cycle 1 and 42 mg/m² on day 8 of cycle 1 and thereafter).

The subject will be considered on protocol treatment while receiving carfilzomib or pomalidomide.

If day 1 of a cycle is delayed, all subsequent doses within the cycle and day 1 of subsequent cycles should be adjusted accordingly to maintain the 28-day cycle duration. However, if a within-cycle dose is delayed, then the dates of the subsequent within-cycle doses should not be adjusted. For within-cycle doses, if administration does not commence within the allowable window of the scheduled administration date, then the dose will be considered a missed dose. Administration may resume at the next planned dosing date. A missed dose will not be made up. There should be a minimum of 5 days between carfilzomib doses.

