If a subject requires interruption of carfilzomib for more than 6 consecutive weeks due to unresolved toxicities, the subject must be discontinued permanently from carfilzomib.

The reason for dose change of carfilzomib is to be recorded on each subject's eCRF.

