Posterior reversible encephalopathy syndrome: Headaches, altered mental status, seizures, visual loss, and hypertension	If PRES is suspected, hold carfilzomib. Consider evaluation with neuroradiological imaging, specifically MRI, for onset of visual or neurological symptoms suggestive of PRES. If PRES is confirmed, permanently discontinue carfilzomib. If the diagnosis of PRES is excluded, carfilzomib administration may resume at same dose, if clinically appropriate.
Progressive multifocal leukoencephalopathy	Patients should be monitored for any new or worsening neurologic, cognitive or behavioral signs, or symptoms that may be suggestive of PML as part of the differential diagnosis of CNS disorders. If PML is suspected, withhold administration of carfilzomib; patients should be promptly referred to a specialist and appropriate diagnostic testing should be initiated. Discontinue carfilzomib if PML diagnosis is confirmed.
Thrombotic microangiopathy: Fever, microangiopathic hemolytic anemia, renal failure, thrombocytopenia, neurological manifestations	If the diagnosis is suspected, hold carfilzomib and manage per standard of care including plasma exchange as clinically appropriate. If TMA is confirmed, permanently discontinue carfilzomib. If the diagnosis is excluded, carfilzomib can be restarted
Venous thrombosis (≥ grade 3)	Hold carfilzomib and adjust anticoagulation regimen; resume at full dose once anticoagulation has been optimized per treating investigator's discretion.
Any other drug-related nonhematologic toxicity ≥ grade 3 ^b	For carfilzomib attribution, hold dose. Resume at 1 dose decrement when toxicity has resolved to grade 1 or less or to baseline grade.

Page 3 of 4

ALT = alanine aminotransferase; ANC = absolute neutrophil count; ARDS = acute respiratory distress syndrome; AST = aspartate aminotransferase; CNS = central nervous system; CrCl = creatinine clearance; DBP = diastolic blood pressure; KRd = carfilzomib in combination with lenalidomide and dexamethasone; LDH = lactate dehydrogenase; MRI = magnetic resonance imaging; NCI-CTCAE = National Cancer Institute-Common Terminology Criteria for Adverse Events; PML = Progressive multifocal leukoencephalopathy; PRES = Posterior Reversible Encephalopathy Syndrome; SBP = systolic blood pressure; TMA = thrombotic microangiopathy; ULN = upper limit of normal.

Table 7-3. Carfilzomib Modification Guidelines for Nonhematologic Toxicities

Page 4 of 4

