7.4.1.2 Non-Amgen Investigational Product: Pomalidomide

Dose reduction levels of pomalidomide for toxicity management of individual subjects are provided in [Table 7-4](#).

Table 7-4. Dose Decrements for Pomalidomide

Nominal Dose ^a	Reduced Pomalidomide Doses (mg/m ²)		
	Dose -1	Dose -2	Dose -3
4 mg	3 mg	2 mg	1 mg

Pomalidomide will be discontinued, temporarily delayed, or dosage temporarily reduced, in the event of a treatment-related toxicity that, in the opinion of the investigator, warrants the discontinuation, temporary delay or dose reduction as indicated in [Table 7-5](#) and [Table 7-6](#).

Table 7-5. Pomalidomide Modification Guidelines for Thrombocytopenia and Neutropenia

	Recommended Action
	Pomalidomide
Neutropenia	
ANC < 500 per mL or ANC < 1000 per μ L with fever $\geq 38.5^{\circ}\text{C}$	Interrupt pomalidomide treatment, follow complete blood count (CBC) weekly, administer myeloid growth factor

Page 1 of 2

Footnotes defined on last page of the table

Table 7-5. Pomalidomide Modification Guidelines for Thrombocytopenia and Neutropenia

	Recommended Action
	Pomalidomide
Neutropenia (continued)	
ANC return to ≥ 500 per μL	Resume pomalidomide at 3 mg daily
For each additional drop < 500 per μL	Interrupt pomalidomide treatment
Return to ≥ 500 per μL	Resume pomalidomide at 1 mg less than the previous dose
Thrombocytopenia	
Platelets $< 25\,000$ per μL	Interrupt pomalidomide treatment, follow CBC weekly
Platelets return to $> 50\,000$ per μL	Resume pomalidomide at 3 mg daily
For each additional drop $< 25\,000$ per μL	Interrupt pomalidomide treatment
Return to $\geq 50\,000$ per mCL	Resume pomalidomide at 1 mg less than the previous dose

Page 2 of 2

ANC = absolute neutrophil count; CBC = complete blood count

Table 7-6. Pomalidomide Modification Guidelines for Nonhematologic Toxicities

Symptom/Sign/Investigation	Recommended Action
	Pomalidomide
Rash = grade 3	Interrupt pomalidomide. Decrease by one dose level when dosing is resumed at next cycle (rash must be resolved or improved to \leq grade 1 before dose resumption).
Rash = grade 4 or blistering (including angioedema, anaphylactic reactions, exfoliative or bullous rash or if Stevens-Johnson Syndrome (SJS), Toxic Epidermal Necrolysis (TEN), or Drug Reaction with Eosinophilia and Systemic Symptoms (DRESS) is suspected.	Permanently discontinue study treatment

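### After a carfilzomib-attributed severe skin or hypersensitivity reaction, Table 7-3 lets carfilzomib resume, although Table 7-6 treats the same reactions as grounds for a permanent stop

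*Protocol*

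**What the plan says.** **Pomalidomide rules.** In Protocol Section 7.4.1.2, Table 7-6 has a row for grade 4 or blistering rash. It extends to angioedema, anaphylactic reactions, exfoliative or bullous rash, and suspected SJS, TEN or DRESS. The action is "Permanently discontinue study treatment". The rows for grade 3 rash and for other grade 3 or higher events name pomalidomide instead.

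**Meaning of the term.** The opening of Section 7 says: "Study treatment is defined as any investigational product(s) or non-investigational product(s) intended to be administered". Section 5.1 adds: "Subjects who discontinue either carfilzomib or pomalidomide, but not both drugs, will be considered to remain on study treatment".

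**Carfilzomib rules.** Section 7.4.1.1 sends carfilzomib decisions to Tables 7-2 and 7-3 and points to Tables 7-5 and 7-6 only "for KPd pomalidomide dosage adjustments". Table 7-3 has no row for the reactions above. Its last row covers any other drug-related nonhematologic toxicity of grade 3 or higher: "For carfilzomib attribution, hold dose. Resume at 1 dose decrement when toxicity has resolved to grade 1 or less or to baseline grade".

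**Re-escalation.** Under Section 7.4.1.1, subjects who "tolerate the reduced dose for 1 full cycle may at the discretion of the treating physician increase the dose to a prior dose", "except when the dose reduction is due to: pulmonary hypertension, pulmonary toxicity, grade 3 or worse cardiac failure, or drug-induced hepatotoxicity". Severe skin and hypersensitivity reactions are not among the exceptions.

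**The concern.** Two tables in one protocol can give different carfilzomib instructions for the same clinical event. A site that looks up carfilzomib in the table it is told to use finds a hold-and-resume instruction. A site that reads Table 7-6 with the defined term finds a permanent stop of the whole regimen.

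At stake is re-exposure to carfilzomib after, for example, an anaphylactic reaction blamed on carfilzomib. The protocol treats hypersensitivity to carfilzomib as foreseeable. Section 7.1.1.1.3 requires infusion at a facility that can manage such reactions, and exclusion criteria 245 and 246 keep out anyone already known to be hypersensitive or allergic. A subject who would be refused entry for a known carfilzomib allergy could be rechallenged after showing one on study.

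**Working it through.** No statistical calculation applies, so the check sets the texts side by side.

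**1. Scope of the Table 7-6 cell.** The Section 7 definition covers investigational and non-investigational products: carfilzomib, pomalidomide and dexamethasone. Under Section 5.1, stopping pomalidomide alone leaves a subject on study treatment. Read literally, the cell therefore stops carfilzomib too. Read by its setting (section, table title and column heading all pomalidomide), it may mean pomalidomide alone. The documents do not settle this.

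**2. Permanent stops in Table 7-3.** There are six: drug-induced hepatotoxicity, heart failure unresolved after 4 weeks, grade 4 neuropathy, and confirmed PRES, PML or TMA. None covers these reactions, so the last row is the only one that can apply.

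**3. Carfilzomib instruction by attribution and grade.**

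| Event | Table 7-3 | Table 7-6, all-drug reading | Table 7-6, pomalidomide-only reading |
|---|---|---|---|
| Grade 3 or higher, attributed to carfilzomib | Hold, then resume one level lower | Permanent stop | Silent, so Table 7-3 governs |
| Grade 3 or higher, attributed to the combination | Unclear: footnote b lists this attribution, but the action is worded for carfilzomib only | Permanent stop | Silent |
| Attributed to pomalidomide alone | No instruction | Permanent stop | Silent |
| Below grade 3, attributed to carfilzomib (e.g. low-grade angioedema) | No instruction | Permanent stop | Silent |

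The first line is the direct clash. The second is a likely one. The last two are gaps in Table 7-3.

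**4. Dose at issue.** From Table 7-1, one decrement from 56 mg/m² is 45 mg/m², and 45/56 = 0.80. With three infusions per cycle in cycles 2 to 12 and two from cycle 13:

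- after the decrement: 3 × 45 = 135 and 2 × 45 = 90 mg/m² per cycle
- after permitted re-escalation: 3 × 56 = 168 and 2 × 56 = 112 mg/m² per cycle
- under the all-drug reading of Table 7-6: 0

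**5. Would another rule catch it?** Section 7.4.1.1 forces a permanent stop in one relevant case: "If a subject requires interruption of carfilzomib for more than 6 consecutive weeks due to unresolved toxicities". A reaction that settles within 6 weeks escapes it. Footnote a to Table 7-1 brings in the medical monitor when a reduction is needed on cycle 1 day 1, but not later.

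**6. The protocol's own practice.** Venous thrombosis has a row in both Table 7-3 and Table 7-6. For hepatitis B reactivation, Section 9.2.4.10.3 interrupts study treatment and Table 7-3 has a matching hold. The severe-reaction row has no such counterpart.

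**The case against.** The best case against this is context. The cell sits among pomalidomide rules, and the Amendment 4 summary says the pomalidomide nonhematologic guidance was updated to match that drug's investigator's brochure. The last row of Table 7-6 concerns other pomalidomide-related events, which suggests the rows above it do as well. On that view pomalidomide stops, carfilzomib follows its own table, and the only flaw is a loose phrase. If the literal term is right instead, a specific permanent stop should prevail over a general catch-all. The tables are also guidelines: the investigator may discontinue carfilzomib for any toxicity that warrants it, and re-escalation is discretionary.

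Much of this stands. It rules out one inference a reader might draw, that the protocol clearly requires all three drugs to stop whatever the cause. The intended scope is uncertain, Section 5.1 expects one drug to continue when the other stops, and Section 7.4.1.3 leaves dexamethasone to the investigator's opinion.

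It does not remove the problem. On the pomalidomide-only reading, Table 7-3 still recommends resuming carfilzomib after a grade 3 or higher reaction attributed to carfilzomib. Nothing says that the named row in Table 7-6 overrides the catch-all, and the pointer in Section 7.4.1.1 steers carfilzomib decisions away from Table 7-6. Discretion permits a stop but does not require one.

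**Conclusion.** The point holds in limited form. When one of these reactions is grade 3 or higher and attributed to carfilzomib, Table 7-3 as written leads to rechallenge and permits later re-escalation. If Table 7-6 covers carfilzomib, the two tables contradict each other. If it covers pomalidomide only, Table 7-3 leaves a safety gap: the same kind of reaction ends one drug for good while the drug actually blamed may be restarted. Combination attribution is left without a clear action.

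Three stronger conclusions may tempt a reader but are not supported:

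- *Every such reaction produces a conflict.* The resume clause needs grade 3 or higher and carfilzomib attribution; otherwise Table 7-3 is silent.
- *Rechallenge is compulsory.* The tables give recommended actions, and the investigator may stop the drug.
- *The efficacy results are compromised.* No endpoint, hypothesis or sample size depends on these rows.

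The difference for one affected subject on 56 mg/m² is 45 mg/m², possibly rising to 56, against no carfilzomib, assuming resolution within the 6-week limit. The documents give neither the incidence of these reactions nor the number of subjects still on treatment. Enrollment ended in late 2021 with 54 enrolled and 52 treated with carfilzomib, so a change protects only those still receiving the drug. Treatment may continue until progression, and the end-of-study visit falls 4 years after the last enrollment. The correction should be made, but it has no bearing on the trial's statistical conclusions.

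**What to change.** 1. In Table 7-3, add a row above the catch-all: *Grade 4 or blistering rash, angioedema, anaphylactic reaction, exfoliative or bullous rash, or suspected SJS, TEN or DRESS, attributed to carfilzomib or to the KPd combination, or where carfilzomib cannot be excluded as a cause: permanently discontinue carfilzomib; do not apply the row below.*
2. In Table 7-6, replace the general term with the drug meant: *Permanently discontinue pomalidomide; for carfilzomib see Table 7-3.* Leave dexamethasone to Section 7.4.1.3.

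If the sponsor did intend all three drugs to stop, the cell should name them, and Table 7-3 and Section 7.4.1.3 should be changed to agree.

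The cost is one added row and one reworded cell, with no change to endpoints, sample size or SAP. The downside is that a few subjects may lose carfilzomib when the cause is uncertain.

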7.4.1.3 Non-Amgen Non-Investigational Product: Dexamethasone

Dexamethasone may be discontinued, temporarily delayed, or dosage temporarily reduced, in the event of a treatment-related toxicity that, in the opinion of the investigator, warrants the discontinuation, temporary delay or dose reduction. Investigators are advised to consult the approved regional labeling for dexamethasone for additional details.

The reason for dose change of dexamethasone is to be recorded on each subject's eCRF.

7.4.2 Hepatotoxicity Stopping and Rechallenge Rules

Refer to Section 7.4.1 for stopping and rechallenging requirements when subjects have abnormal hepatic laboratory values (ie, AST, ALT, total bilirubin) and/or signs/symptoms of hepatitis. Carfilzomib should be discontinued for drug-induced hepatotoxicity attributable to carfilzomib.

7.5 Preparation/Handling/Storage/Accountability

Guidance and information on preparation, handling, storage, accountability, destruction, or return of the investigational product and/or other protocol-required therapies during the study are provided in the IPIM.

7.6 Treatment Compliance

Administration of IV medicinal products will occur at the study center. Oral medication may be dispensed for self-administration at home. Subjects are to document all administered doses and missed doses in a medication diary for all study-required medication taken at home.

7.7 Treatment of Overdose

None of the investigational products in this study have specific antidotes. Therapy for overdose involves monitoring and management of acute side effects until the subject is stable.

7.8 Prior and Concomitant Treatment

7.8.1 Prior Treatment

Prior therapies for multiple myeloma must date back to the original diagnosis and will be collected on the Prior Multiple Myeloma Therapy eCRF. For subjects who are being referred to the research site, critical referral information will constitute multiple myeloma information from source notes. Prior lines of multiple myeloma treatment are defined as a planned course of therapy. Therefore, during initial treatment, the induction

± autologous stem cell transplant ± consolidation and maintenance would be considered 1 line of therapy (see Section 12.8 for additional guidance on lines of therapy).

For prior antimyeloma therapies, collect transplant, best response, did subject relapse/progress on or after this regimen, date of relapse/progression, drug name, reason for therapy, start date, stop date, reason medication was stopped.

Prior therapies for non-multiple myeloma conditions that were being taken/used from 30 days prior to signing of the ICF will be collected on the Concomitant Medications eCRF. Collect therapy name, indication, dose, unit, frequency, start and stop dates.

7.8.2 Concomitant Treatment

Throughout the study, investigators may prescribe any concomitant medications or treatments deemed necessary to provide adequate supportive care except for those listed in Section 7.1.7.

Concomitant therapies are to be collected from informed consent through the 30 days after the last dose of all study drug(s). For all concomitant therapies, collect therapy name, indication, dose, unit, frequency, start and stop dates and record on Concomitant Medications eCRF.

It is recommended to follow the Eighth Joint National Committee 2014 and 2018 ESC/ESH evidence-based guidelines for the management of high blood pressure in adults (Williams et al, 2018; James et al, 2014; and Section 12.10).

8. Discontinuation Criteria

Subjects have the right to withdraw from investigational product and/or other protocol-required therapies, protocol procedures, or the study as a whole at any time and for any reason without prejudice to their future medical care by the physician or at the institution.

The investigator and/or sponsor can decide to withdraw a subject(s) from investigational product, device, and/or other protocol-required therapies, protocol procedures, or the study as a whole at any time prior to study completion for the reasons listed in Sections 8.1, 8.2.1, and 8.2.2.

8.1 Discontinuation of Study Treatment

Subjects (or a legally acceptable representative) can decline to continue receiving investigational product and/or other protocol-required therapies or procedures at any time during the study but continue participation in the study. If this occurs, the

investigator is to discuss with the subject the appropriate processes for discontinuation from investigational product or other protocol-required therapies and must discuss with the subject the possibilities for continuation of the Schedule of Activities (see [Table 2-1](#)) including different options of follow-up (eg, in person, by phone/mail, through family/friends, in correspondence/communication with other treating physicians, from the review of medical records) and collection of data, including endpoints, adverse events, and must document this decision in the subject's medical records. Subjects who have discontinued investigational product and/or other protocol-required therapies or procedures should not be automatically removed from the study. Whenever safe and feasible, it is imperative that subjects remain on-study to ensure safety surveillance and/or collection of outcome data.

Reasons for removal from protocol-required investigational product(s) or procedural assessments include any of the following:

- decision by investigator or sponsor
- lost to follow-up
- death
- ineligibility determined
- protocol deviation
- non-compliance
- adverse event
- subject request
- disease progression
- pregnancy

